#### 9. PREMATURE WITHDRAWAL OF PARTICIPANTS FROM STUDY

Participants may withdraw from the study at any time for any reason. Participants may be excluded from the study by the investigator due to failure of participant to comply with study procedures. In the event that a participant withdraws from the study voluntarily or is withdrawn by the investigator, it will be reported in the study file and will be documented appropriately. It will also be considered accordingly in the statistical analyses.

The participant will be discontinued from further study participation if:

- The participants oxygen saturation falls to <80% continuously for >15 seconds.
- A clinical adverse event occurs suggesting that:
  - The participant's health may be in jeopardy from continued participation in the study;

OR

- The participant is unable to complete the study procedures successfully.
- The participant withdraws voluntarily from the study at any time.

Participants who discontinue from the study for reasons unrelated to the study (e.g. personal reasons) will be replaced as required for the study to meet its objectives.

DATE: November 15, 2024

#### 11. APPENDICES FOR PART I

# **Appendix I Guidelines for Spirometry Testing**

# **Equipment Calibration**

Calibration and maintenance logs must be maintained for the body plethysmograph and the hand-held spirometer. Calibration must be performed on days when there is a study visit or weekly, whichever is more often.

# **Procedures**

In order to assure acceptable spirometry data with a sufficient level of accuracy and precision, the technician should coach each participant to perform maximal expiratory maneuvers with each measurement. The technician should pay special attention to ensure that the participant:

- Takes a full, deep breath (i.e., to total lung capacity) with nose clip in place (or nose pinched closed with thumb and forefinger) and has a tight seal with his/her lips around the mouthpiece.
- Blows out forcefully, without hesitation; and
- Continues exhalation with sufficient effort until all air is exhaled;
- Is coached continually during the maneuver by the technician (e.g., "BLOW OUT HARD...BLOW...") to assure maximum effort (but not to the point of syncope).

# **Maneuver Acceptability Criteria**

A spirometry measurement will be judged acceptable when it conforms to ATS standards for acceptability. These criteria include:

- Adequate start of the test.
- Adequate expiratory time (at least 6 seconds).
- Adequate "time to" peak flow.
- No evidence of interruption by coughing, glottis closure, obstruction by tongue or false teeth.

The achievement of ATS reproducibility criteria will be the overall goal. This will be defined as: the best 2 acceptable spirograms have FEV1 values that do not vary by more than 5% of the largest value or more than 100 mL, whichever is greater.

However, it is understood that reproducibility criteria in participants with respiratory disease is difficult to achieve. Thus, it is recognized that some participants, by giving maximal effort, become increasingly fatigued on each subsequent maneuver. In this case, fewer than 3 maneuvers are allowed; the first FEV1 will be considered the best.

# **Reporting of Data**

For the purpose of analysis, the largest FEV1 and the largest FVC from the acceptable and reproducible maneuvers (regardless of whether they were obtained from the same curve or not) will be considered the true value for that series of measurements.

At the end of each spirometry test, a hardcopy printout of the data should be produced as described in the instrument manual. The original printout of the measurements will serve as the source documents for these data.

DATE: November 15, 2024

# **Appendix II Guidelines for Plethysmography**

# **Equipment Calibration**

Calibration and maintenance logs must be maintained for the body plethysmograph. Calibration must be performed on days when there is a study visit or weekly, whichever is more often.

# **Procedures**

At each visit, the qualified investigator or other qualified site personnel will explain and demonstrate the test maneuver. The investigator or other site personnel will perform the procedure according to the manufacturer's guidelines. Lung volume measurements to be collected include but are not limited to: TLC and FRC. To determine the functional integrity of the alveolar-capillary membrane, a test to measure DLco will be performed.

Procedures for these measurements include the following:

- Participant will be seated upright and breathing movements should not be restricted by clothing.
- Participant will place the mouthpiece in their mouth and a nose clip on the nose.
- The participant will perform several tidal breaths to initiate the process and will be instructed to exhale slowly. At the end-exhalation the participant valve will close for start of inspiration.
- After the mouth shutter closes, the participant will be instructed to gently "pant" (approximately 50 to 60 mL of air). Pant frequency should be approximately 1 Hz. The cheeks and chin should be supported with both hands. This should be done without supporting the elbows or elevating the shoulders.
- The shutter should only be closed for about 2 seconds, to avoid undue participant discomfort.
- Lung volume measurements (inspiratory capacity (IC), slow vital capacity (SVC), etc.) may be measured immediately after the shutter is reopened and before coming off the mouthpiece. If the participant is too short of breath, the lung volume measurements may be performed after a brief rest period.
- At least 3 separate, acceptable maneuvers should be performed.
- The result from this effort is displayed on the computer screen displaying the pressure vs. time tracing.
- To measure DLco, the participant will perform several tidal breaths to initiate the
  process. Participant should then be instructed to exhale slowly and maximally to
  residual volume. At the end of the exhalation, the participant valve will be closed
  for the start of inspiration and the participant circuit will open to the source of gas.
  The participant will then inhale through the mouthpiece a special diffusion gas
  mixture containing neon, oxygen, nitrogen and carbon monoxide.
- The participant will hold his or her breath at TLC for 6 seconds. The participant will be instructed to relax against the closed valve for this period. When the valve opens, the participant will be instructed to exhale rapidly until the sample is collected. The test will then end and the participant can relax and remove the nose clips.

DATE: November 15, 2024

The gas sample is collected automatically into the chromatograph for analysis.
Once the results from this effort are displayed on the computer screen, the system
is ready for additional efforts. At least 2 separate, acceptable maneuvers should
be performed, allowing four minute interval between efforts. The results of the two
efforts should agree within 10%.

# **Maneuver Acceptability Criteria**

An acceptable thoracic gas volume (TGV) maneuver is defined as

- Proper panting technique is achieved as indicated by the tracing (the loop generated against a closed shutter should be closed or nearly so).
- Recorded pressure changes are within the calibrated pressure range of each transducer and that no leaks are evident.
- The entire tracing should be visible.
- Evidence of thermal equilibrium (i.e. tracings do not drift on the display or recording).
- If all data points lie within 5% of the mean TGV, these trials are considered "acceptable". Continue trials until at least 3 separate, acceptable trials are achieved. Up to a maximum of 8 trials should be performed for a given visit. NOTE: The mean TGV will be reported as the mean of all acceptable trials.

Multiple SVC measurement should be performed with the 2 largest measurements agreeing within 200 mL. The largest SVC measurement will be recorded. The mean values for IC should be recorded and the measurements should agree within 5% of the mean.

An acceptable DLco maneuver is defined as:

- The participant does not begin to inhale before the valving system is activated or the participant's inspired volume will not be measured correctly.
- If results of two efforts are within 10% these trials are considered "acceptable. A third effort should be attempted if the first two efforts are not reproducible.

# **Reporting of Data**

At the end of each pulmonary function test, a hardcopy printout of the data should be produced as described in the instrument manual. The original printout of the measurements will serve as the source documents for these data.

Protocol ROB0037, Robarts Research Institute Version 16

DATE: November 15, 2024

# **Appendix III Guidelines for MBNW**

#### **Equipment Calibration**

The machine will determine environmental conditions and auto-calibrate.

#### **Procedures**

In order to ensure acceptable MBNW data with a sufficient level of accuracy and precision, the technician should coach each participant. The technician should pay special attention to ensure that the participant:

• Has nose clip in place (or nose pinched closed with thumb and forefinger) and has a tight seal with his/her lips around the mouthpiece.

# Maneuver Acceptability Criteria

A MBNW measurement will be judged acceptable when it conforms to ERS/ATS standards for acceptability. These criteria include:

- Adequate start of the test.
- Adequate SVC measurement.
- Regular breathing pattern throughout test.
- No evidence of interruption by coughing, glottis closure, obstruction by tongue or false teeth.

However, it is understood that reproducibility criteria in participants with respiratory disease is difficult to achieve. Thus, it is recognized that some participants, by giving maximal effort, become increasingly fatigued on each subsequent maneuver. In this case, fewer than 3 maneuvers are allowed; the first MBNW test will be considered the best.

#### **Reporting of Data**

For the purpose of analysis, the mean LCI from the acceptable and reproducible maneuvers will be considered the true value for that series of measurements.

At the end of each MBNW test, a hardcopy printout of the data should be produced as described in the instrument manual. The original printout of the measurements will serve as the source documents for these data.

DATE: November 15, 2024

## Appendix IV Guidelines for FOT

## **Equipment Calibration**

Device verification must be conducted on each day of use prior to initiating a Patient Test. The verification tests confirm that the calibrated parameters and performance characteristics fall within expected values for a reference load. The automated Test Load Calibration Wizard will guide the operator through the necessary sequence and displays a PASS/FAIL result for two verification tests: (1) Static Check, and (2) Frequency Sweep. Both verification tests must pass prior to measuring a patient. Successful verification results are valid for 24 hours.

### **Procedures**

In order to ensure high quality and repeatable FOT data, the technician should follow a standard measurement sequence, allowing for an initial start-up time where the patient can familiarize his/herself with the device and oscillating airwaves. The recommended measurement sequence is as follows:

- Seat the patient in an upright position and ensure breathing is not restricted at the neck due to chin position or clothing. If required for research purposes, the measurements can also be done in the supine position, but the impedance values are then indicated as for the supine position.
- Connect a disposable, anti-viral/bacterial filter to the device. Ask the patient to block their nasal passage with a noseclip and place the mouthpiece in their mouth. Patients should gently rest their lips on the mouthpiece and avoid contacting the mouthpiece with any force with their teeth – avoid biting.
- Monitor the patient's normal breathing (no oscillating airwave) to ensure tidal breathing is even and stable. Typically, 5 to 10 seconds is sufficient. Coach the patient to support their cheeks and soft parts below the chin with both hands while breathing to prevent motion of the cheeks. This should be done without supporting the elbows or elevating the shoulders.
- Press either the left or right hand held button to activate an oscillating airwave and capture a recording. Allow the waveform to completely finish before removing the device from the patient's mouth. Typical waveforms run for 16 seconds.
- Provide the patient with a short break of 10 to 30 seconds, during which they may remove their mouth from the device and breathe naturally.
- Begin monitoring your patient once again and capture additional measurements.
- The results and repeatability are provided on the screen for brief evaluation after each measurement.
- Capture a minimum of 3-4 consistent measurements.
- The participant can come off the device at any time for any discomfort or if they need to cough or talk, but then the measurement will need to be repeated.

### **Acceptability Criteria**

An FOT measurement and Patient Test result will be judged acceptable when they conform to the ERS guidelines for reproducibility and meet the following criteria:

Coherence of outcomes Rrs and Xrs at each frequency of interest (i.e. R6, R19, X6, and X19, where for example, R6 means Rrs at 6 Hz) must exceed 90% for each measurement.

DATE: November 15, 2024

Coherence less than 90% can indicate that noise has contaminated the measurement. The coherence is indicated by the software.

 Coefficient of variation (CV) for Rrs and Xrs at each frequency of interests for the final array of successful measurements must NOT exceed 15%. CV is provided by the software.

It is acceptable to exclude whole or part measurements to achieve the above stated acceptability criteria. Exclusion may be conducted in two ways:

- Dataset Delimiting may be used to select portions of a measurement containing artefacts such as a cough, swallow or talking to be excluded from analysis.
- Whole measurements representing clear outliers and/or unsuccessful trials such as due to excessive coughing or coming off the device during measurement may be excluded by checking the 'Exclude' box on the measurement card in Results View.

The operator is recommended to ensure that averaged outcomes are calculated on a minimum of 3 satisfactory measurements.

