# 4.1.4. Forced Oscillation Technique (FOT)

FOT (Appendix IV) will be performed on all participants at each visit using the "tremoFlo™" Airwave Oscillometry System (THORASYS Thoracic Medical Systems, Montreal, QC). FOT is a method for measuring lung function without patient effort. FOT functions by superimposing a gentle multi-frequency airwave onto the patient's normal respiratory airflow while measures of airway impedance are acquired through the analysis of resulting pressure and flow signals. Participants breathe naturally throughout the measurement sequence, which comprises of at least 3 measurements of 16 seconds

DATE: November 15, 2024

each. Airwaves comprise of small amplitude pressure oscillations (<2 cm H2O peak to peak) well below the acceptable limits of 5 cmH2O, which are far below attainable physiological normal transpulmonary pressures. Airwaves are specifically designed for performance with carefully selected frequencies between 5 and 38 Hz, with a commonly used waveform including of 6, 11 and 19 Hz. These are experienced by the participants as very small flutters during breathing and are easily tolerated. Device verification will be conducted on each day of use to confirm calibration parameters and performance characteristics fall within expected values for a reference load.

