#### 7. STUDY PARAMETERS

#### 7.1. Evaluation of Disease

# 7.1.1. Pulmonary Function Testing

The FEV1 and FVC will be recorded according to ATS guidelines. Parameters to be assessed include but are not limited to: total lung capacity (TLC), functional residual capacity (FRC) and DLco. FRC measures the volume in the lungs when the muscles of respiration are relaxed. FOT measurements will be recorded according to ERS recommendations (Oostveen et al., Eur Respir J 2003; 22: 1026–1041). Input impedance is calculated as the ratio of pressure and flow signals and are given as Rrs and reactance Xrs at each oscillation frequency as well as comparison to predicted values. Additional outcomes that are provided from this measurement include tidal volume, respiratory rate, and resonant frequency.

Frequency dependence of Rrs is an index of ventilation heterogeneity, and low frequency reactance (6 Hz) can be used as an index of airway closure (Lutchen et al., 20xx) and we are investigating if this corresponds to the occurrence of ventilation defects. We will assess the frequency dependence by subtracting Rrs at 19 Hz from Rrs at 6 Hz. Furthermore, low frequency elastance at 6 Hz can be used as an index of airway closure indicative of the presence of low or near zero ventilation.

FeNO will be measured one time according to instructions from the machine which is set to perform to ATS guidelines. The FeNO value will be displayed on the machine and recorded in source documents, it is a valuable tool in the assessment of airway inflammation.

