### **Reporting of Data**

For the purpose of analysis, the averaged results from only the acceptable and reproducible measurements will be considered valid for a Patient Test. Excluded datasets and/or reporting intervals will not be included in the final averaged values. At the end of each FOT Patient Test, a hardcopy printout of the data should be produced. The original printout of the test results will serve as the source documents for these data.

DATE: November 15, 2024

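### The 15% CV limit for FOT acceptability is applied to signed reactance (X6, X19) as well as resistance, so tests with small reactance can fail for closeness to zero rather than poor repeatability

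*Protocol*

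**What the plan says.** Protocol Appendix IV (Guidelines for FOT), Acceptability Criteria, sets two numerical conditions.

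- **Coherence.** "Coherence of outcomes Rrs and Xrs at each frequency of interest" must exceed 90%. The same bullet lists the outcomes meant: R6, R19, X6 and X19.
- **CV.** For both Rrs and Xrs, the CV "at each frequency of interests for the final array of successful measurements must NOT exceed 15" percent. There is no exception or alternative limit for values near zero, and no statement of how the CV is formed when the mean is negative.

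The section then states: "It is acceptable to exclude whole or part measurements to achieve the above stated acceptability criteria". Two routes are given: cutting out portions with artefacts such as a cough, swallow or talking, and dropping whole measurements that are clear outliers or unsuccessful trials. Operators are advised that "averaged outcomes are calculated on a minimum of 3 satisfactory measurements".

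Under Reporting of Data, "the averaged results from only the acceptable and reproducible measurements will be considered valid for a Patient Test".

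Section 7.1.1 says that "low frequency reactance (6 Hz) can be used as an index of airway closure" and that the study is investigating whether this corresponds to ventilation defects. It also plans R6 minus R19 as the measure of frequency dependence, and adds: "Additional outcomes that are provided from this measurement include tidal volume, respiratory rate, and resonant frequency". Section 2 makes the relation of oscillometry to 129Xe MRI abnormalities a study objective.

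**The concern.** A CV is the SD divided by the mean. It measures repeatability only when the mean is well away from zero. Rrs meets that condition. Xrs need not: it changes sign, and the resonant frequency that the protocol records is the frequency at which it is zero.

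If X6 or X19 is small for a participant, the ratio is large however closely the readings agree. Two participants with the same absolute scatter are then judged differently only because one has the smaller |Xrs|. Because the criterion decides which results count as valid, it selects on the value of the outcome.

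For X6 the selection removes the values nearest zero. X6 is the variable to be set against ventilation defects, so its mean, its spread and its correlation with MRI measures can all be affected. If an Xrs failure is taken to invalidate the whole patient test, sound R6 and R19 values are lost too.

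**Working it through.** The protocol states no derivation for the 15% limit, so there is no figure to reproduce. The check asks how the rule behaves.

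**Inputs from the protocol:** limit c = 0.15; minimum n = 3 readings; outcomes X6 and X19. **Assumed, because the protocol gives none:** the true mean Xrs (mu), its within-test SD (s) and the between-person distribution of X6. Readings are taken as normal, and the CV as sample SD divided by |sample mean|.

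**One test.** With three normal readings, the sample SD falls below k times s with probability 1 - exp(-k^2), independently of the sample mean. Setting k = 0.15 x |sample mean|/s and averaging over the sample mean, with r = mu/s, v = 1/3 and D = 1 + 2(0.0225)v = 1.015:

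- P(pass) = 1 - D^(-1/2) x exp(-0.0225 r^2 / D)
- retained mean / true mean = [1 - D^(-3/2) x exp(-0.0225 r^2 / D)] / P(pass)

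For r = 5: 0.0225 x 25 / 1.015 = 0.554; exp(-0.554) = 0.5745; D^(-1/2) = 0.9926; P = 1 - 0.570 = 0.430.

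| abs(mean)/SD | Pass | Shift of retained mean away from zero |
|---|---|---|
| 0 | 0.7% | undefined |
| 1 | 3% | 49% |
| 2 | 9% | 15% |
| 2.5 | 14% | 9% |
| 3 | 19% | 6% |
| 5 | 43% | 2% |
| 10 | 89% | 0.2% |
| 15 | 99.3% | below 0.1% |

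Simulation agrees. With four readings the pattern is similar (4%, 36% and 92% pass at ratios 2, 5 and 10).

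**Same precision, different verdict.** With an assumed SD of 0.2 for each outcome: Rrs = 3.0 (ratio 15) passes 99.3% of the time; X6 = -1.0 (ratio 5) passes 43%; X19 = 0.3 (ratio 1.5) passes 5.6%, with a retained mean of 0.375.

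**Across participants.** Let true X6 be normal with mean M and between-person SD T. The same formulas hold with r = M/s and v = T^2/s^2 + 1/3. For M = -1, T = 0.5, s = 0.2: v = 6.583, D = 1.296, P = 0.431, and the retained mean is -1.30, which is 30% too negative. Each cell shows the share passing, the retained mean, and its excess over the true mean:

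| X6 mean / SD between people | s = 0.1 | s = 0.2 | s = 0.3 |
|---|---|---|---|
| -1.0 / 0.5 | 76%; -1.17; 17% | 43%; -1.30; 30% | 25%; -1.37; 37% |
| -1.5 / 1.0 | 83%; -1.75; 17% | 62%; -1.99; 32% | 44%; -2.15; 43% |
| -2.5 / 1.5 | 92%; -2.71; 8% | 80%; -2.94; 18% | 67%; -3.15; 26% |

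Most of this shift comes from which participants are retained, not from bias within a test.

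**Choosing readings to meet the limit.** Taking the best 3 of 5 readings at ratio 2 raises the pass rate from 9% to 48%, but the retained mean is still about 14% too far from zero.

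**The case against.** - **The rule does not cover every frequency.** Section 4.1.4 describes "carefully selected frequencies between 5 and 38 Hz, with a commonly used waveform including of 6, 11 and 19 Hz", and a reader might infer that the limit must fail wherever the zero crossing lies. It binds only at 6 and 19 Hz. This stands: resonance matters only if it leaves X6 or X19 small relative to its scatter.
- **Nothing in the protocol places X6 or X19 near zero.** A reader might infer that good tests are generally being lost and that the retained reactance is known to be biased. The documents do not support that. At |mean|/SD of 10 or more, about 89% or more of tests pass and within-test bias is negligible.
- **Exclusion is not a free choice of readings.** The two permitted routes are mostly tied to artefacts. What remains value-based is the undefined clear-outlier ground and the stated purpose of reaching the limits.
- **The technician sees repeatability after each reading and can take more.** The fixed-three pass rates therefore overstate lost tests. Choosing among readings does not remove the shift, however.
- **Loss of R6 minus R19 is a possible reading, not a stated rule.** Appendix IV speaks of the patient test result but does not say that an Xrs failure voids the Rrs values.
- **The stakes are limited.** The study is exploratory, FOT is not among the main efficacy parameters in the synopsis, and Section 8 names no FOT model. Even so, oscillometry has its own objective and Section 7.1.1 ties X6 to ventilation defects.

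**Conclusion.** The point holds in a limited form. As written, one relative limit is applied to a signed quantity and used as a condition of validity, with no provision for values near zero. Where |X6| or |X19| is small relative to its within-test SD, the CV reflects closeness to zero, equally precise tests fail, and retained values are pushed away from zero.

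The size cannot be fixed from the protocol. Under the assumed X6 populations and within-test SDs of 0.1 to 0.3, the pass rate runs from 25% to 92% and the retained mean is 8% to 43% too negative. Better repeatability or X6 further from zero would shrink the effect. These figures assume normal readings, a fixed set of three and a CV based on the absolute mean.

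That last assumption needs an answer. If the software divides by the signed mean, every negative mean Xrs meets the limit automatically and the criterion does no work for X6. That is a different fault in the same sentence.

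**What to change.** Revise Appendix IV as follows.

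1. Keep the 15% CV limit for Rrs only.
2. Accept Xrs on coherence above 90% plus an absolute between-reading SD limit in the units of Xrs. Set the limit once from the study's own pooled repeat readings, without reference to MRI results. As a guide, with three normal readings a limit of 1.73 times the pooled within-test SD passes 1 - exp(-1.73^2) = 95% of tests at any mean, including zero. The retained mean is then unbiased, because the sample mean and SD are independent.
3. Judge Rrs and Xrs separately, so that an Xrs failure does not void R6 minus R19.
4. Remove the purpose clause and the clear-outlier ground from the exclusion text. Allow exclusion only for a recorded artefact, using those already listed.
5. State how the software computes the CV when the mean is negative.
6. Re-score earlier tests where individual readings can be retrieved.

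The cost is about one paragraph of text, one pooled-SD calculation and the re-scoring. Re-scoring may be incomplete, since the source document is a printout and the study dates from 2013. Slightly noisier Xrs values will be retained.
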